3 OBJECTIVES

3.1 Study Objectives

Primary: The primary objective is to quantify the difference in proportion of SOCLs treated operatively when a diagnostic device is used compared to when one is not used and to quantify the difference in proportion of SOCLs treated surgically that extend into dentin when a diagnostic device is used compared to when one is not used.

Secondary: The secondary objectives are to identify the clinical characteristics of SOCLs that best predict caries that extends into dentin, to determine whether the principal factors used by participating practitioners in managing SOCLs change when a caries detection device is employed, and to obtain practitioners' assessments of the utility of the devices in their practices. Because the vignettes are designed to simulate the clinical situations for which data collection will occur, their fidelity in predicting practitioners' treatment decisions will also be assessed, providing a unique and needed insight into their utility for future studies of diagnostic decision-making.

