11.3 Final Analysis Plan

This is the planned analysis based on the data we plan to collect. An appropriate statistical model must take into account both the level of measurement of the outcome variables and the study design. Both of the primary outcome variables, surgical treatment of the lesion and extension into dentin, may be appropriately represented as dichotomous variables. Each practitioner will be randomized to use a single device, or no device and no a priori study design levels defined within the level of practitioner. This approach yields a two-level hierarchical study design. A characteristic of this two-level model is the presence of correlation among the multiple observations obtained from each practitioner. The primary analysis framework will be based on mixed-model logistic regression analysis, implemented with generalized estimating equations (GEE), accounting for correlation among the clusters of observations made by the same practitioners. These models will include a term representing the individual practitioner as a random effect and study arm as a fixed effect. Additional control variables, including region, may be included if it is found that these are needed to account for possibly different distributions of practitioner or patient characteristics. Details of the analysis approach and related considerations are provided in Appendix E

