Appendix E: Statistical Analysis

The primary analysis framework will be based on mixed-model logistic regression analysis, implemented with generalized estimating equations (GEE) to account for correlation among the clusters of observations made by the same practitioners and to provide valid comparisons among the study groups.

Initial exploratory analyses will be conducted for the entire study data set, in order to characterize the empirical distributions of each variable, to identify possible errors in the data, and to evaluate the proportion of missing values. Since the data for Specific Aims 1 through 3 are collected at a single time point, patient-level missing values are anticipated to be unlikely, compared to concerns that arise in studies that include follow-up. If a patient rescinds consent during the study procedures, the practitioner can recruit a replacement patient, as this will not affect the randomized intervention assignment.

The analyses will include all observations that have valid values for the variables in each of the respective analyses. No attempt to replace or impute values that are missing is planned, as this would require assumptions related to the associations that are to be investigated, and could allow pre-analysis expectations to influence the study findings. If a substantial number of missing values is observed, the distribution of these will be evaluated in order to determine whether the missingness can be reasonably assumed to be at random. If this situation holds, then missing values would reduce power, but would not bias the estimates. If missing values are found to occur non-randomly, then the mechanism leading to missing values must be taken into account in the analysis model, for instance, by including variables that are found to be related to missingness. The proposed sample size anticipates that some values may not be obtained, and provides for adequate power despite having up to approximately 20% of observations having missing values for some variables, depending on the differences and level of ICC that are actually observed in the study.

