For evaluation of differences in proportions of lesions treated operatively among the intervention groups, the analysis data set will include all SOCLs that are enrolled by the study practitioners. The outcome variable for this analysis will be a dichotomous variable indicating whether the SOCL was treated operatively. Proportions of SOCL treated operatively will be calculated for each study arm. Confidence intervals, adjusted for correlation within clusters (practitioners), will be estimated from the GEE models. Statistical tests for differences in proportions among the three study arms will be based on Type III tests from the GEE analysis, controlling for the effect of clustering by practitioner. An indicator variable representing the study arm will be included as a fixed effect in this model, and a term representing the individual practitioners will be included as a random effect. The effect of regional site will be evaluated as a fixed effect, and will be included in the model if it explains a statistically significant portion of the observed variation in the outcome variable. The two pre-planned comparisons of the device versus no-device arms will be evaluated using contrasts, and will be tested using Chi-square tests of score statistics. Because these are pre-planned comparisons, each of these tests will be conducted at the 95% confidence level, using per-comparison error rates.

For the comparison of proportions of lesions treated operatively that have caries extending into dentin, the analysis data set will include all SOCLs that were treated operatively by the study practitioners. The outcome variable will be a dichotomous variable indicating whether the lesion extended into the dentin. The analysis will be identical to that utilized for Aim 1, except for the reduced analytic sample. GEE-based mixed-model logistic regression will be used to estimate confidence intervals for proportions of SOCLs extending into dentin, controlling for clustering by

practitioner and, if needed, for regional differences. Two pre-planned comparisons will be conducted using contrasts to compare each of the device study arms with the no-device arm.

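### The primary logistic model is worded as both a GEE and a practitioner random-effect model; one must be named, though the effect on results is modest

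*Protocol*

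**What the plan says.** Section 11.3 gives the primary framework as "mixed-model logistic regression analysis, implemented with generalized estimating equations (GEE), accounting for correlation among the clusters". It continues: "These models will include a term representing the individual practitioner as a random effect and study arm as a fixed effect". It sends the reader to Appendix E for detail.

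Appendix E keeps both halves:

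- Its opening paragraph again describes "mixed-model logistic regression analysis, implemented with generalized estimating equations (GEE) to account for correlation among the clusters".
- For operative treatment: "Confidence intervals, adjusted for correlation within clusters (practitioners), will be estimated from the GEE models". The three-arm test "will be based on Type III tests from the GEE analysis, controlling for the effect of clustering by practitioner", and the two device contrasts "will be tested using Chi-square tests of score statistics". In that same model, "a term representing the individual practitioners will be included as a random effect".
- For dentin extension, the analysis is said to be the same apart from the smaller sample, and the model is again labelled both GEE-based and mixed.
- The model for clinical predictors of dentin extension combines GEE and a practitioner random effect once more.

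On the target quantity, Section 3.1 states: "The primary objective is to quantify the difference in proportion of SOCLs treated operatively when a diagnostic device is used". Section 11.1 also frames the objective as a difference in proportions.

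On covariates, Section 4 stratifies randomisation by region, but Appendix E keeps region in the model only if it is statistically significant. Practitioners' pre-intervention opening rates appear only in exploratory analyses.

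**The concern.** Logistic GEE handles clustering through a working correlation and a robust variance. It has no random-effect term, and its coefficients compare population averages. A logistic model with a practitioner random intercept is fitted by likelihood or an approximation to it, and its coefficients compare arms for a practitioner of given propensity. Under a logit link the two differ whenever practitioners vary.

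The text asks for both at once, in the primary model, and repeats this in each place where the model is described. It is therefore neither a slip in one sentence nor a detail left to an analysis plan: the protocol fixes something that cannot be fitted literally. The choice between two models is left open, and Section 15.4 anticipates no masking, so it could be made with results by arm in view.

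The dentin outcome raises a related question. Each practitioner's cluster size is the number of lesions he or she opened, which is the other primary outcome. If opening tendency and dentin yield are related, the way a model weights practitioners affects the proportion it estimates.

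**Working it through.** **1. The plan's own figure.** Inputs from Section 11.2: 30 practitioners with 20 lesions each per arm, 50% versus 35% opened, ICC 0.05, two-sided chi-square with a Bonferroni-type adjustment for two comparisons (0.05/2 = 0.025).

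- Design effect: 1 + (20 − 1) × 0.05 = 1.95.
- Effective sample: 600/1.95 = 307.7 per arm (stated: 308).
- Power: 93.8%, or 92.8% with a continuity correction (stated: about 92%).

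The figure reproduces. It uses a design effect and a chi-square test, so it does not depend on which logistic model is chosen.

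**2. Operative treatment: marginal against conditional odds ratio.** Let a practitioner's opening probability be expit(η + σZ), with Z standard normal. The marginal proportion is p(η) = E[expit(η + σZ)].

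- Choose σ so that Var[expit(σZ)]/(0.5 × 0.5) equals the ICC in the 50% arm, where η = 0.
- Keep that σ and solve p(η) = 0.35 for the device arm.
- The conditional odds ratio is exp(η). The marginal odds ratio is (0.35/0.65)/(0.50/0.50) = 0.538, with log −0.619.

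At ICC 0.05: σ = 0.470, η = −0.651, exp(η) = 0.522, and 0.651/0.619 = 1.05.

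| ICC | Conditional OR | Marginal OR | Log OR larger by |
|---|---|---|---|
| 0.01 | 0.535 | 0.538 | 1% |
| 0.02 | 0.532 | 0.538 | 2% |
| 0.05 | 0.522 | 0.538 | 5% |
| 0.10 (above plan) | 0.504 | 0.538 | 11% |
| 0.20 (above plan) | 0.463 | 0.538 | 25% |

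Section 11.2 plans for ICCs from 0 to 0.05; the last two rows are assumptions outside that range. With no arm effect, both odds ratios equal 1.

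**3. Dentin extension: weighting of practitioners.** Let u = σZ be the opening tendency from step 2, and let dentin log-odds be slope × u, equal in the two arms. The slope is an assumption, with range −0.5 to −1; the protocol gives no value. Compare the plain average over practitioners, E[expit(slope × u)] = 50%, with the lesion-weighted proportion, in which each practitioner is weighted by the expected number of lesions opened.

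| ICC | Slope | Shift, 50%-opening arm | Shift, 35%-opening arm | Shift in between-arm difference |
|---|---|---|---|---|
| 0.05 | −0.5 | −1.3 | −1.7 | 0.4 points |
| 0.05 | −1 | −2.5 | −3.3 | 0.8 points |
| 0.20 (above plan) | −0.5 | −5.8 | −7.6 | 1.8 points |
| 0.20 (above plan) | −1 | −10.0 | −13.1 | 3.1 points |

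Most of the shift within an arm cancels in the comparison between arms, which is the objective.

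**4. Which model the text supports.** Confidence intervals, the omnibus test and the score contrasts are all attributed to GEE or are usual GEE outputs. No likelihood, integration method or variance component is named. The objective is on the proportion scale. Only the mixed-model label and the random-effect sentences point the other way.

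**The case against.** The strongest defence is that the protocol settles the method in practice. For operative treatment every inferential result comes from GEE, the dentin analysis is meant to follow it, and the random-effect wording may simply be a loose name for the clustering unit. Removing it leaves an analysis that runs. This stands as a limit on the consequence. It does not remove the contradiction, because the random effect is stated as a model term in several places and a later analysis plan would have to override it.

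Some stronger readings are tempting but unsupported:

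- *The primary analysis cannot be run at all, or two analysts must reach materially different answers.* The GEE outputs in Appendix E point clearly to one model, and within the planned ICC range the log odds ratios differ by at most about 5%.
- *A mixed model cannot address the objective.* It can give marginal proportions by averaging over the random effect. The protocol just does not describe that step.
- *The practitioner term would be aliased with arm.* That would apply to a fixed practitioner term, which the protocol never proposes.
- *The dentin result could move by several points.* At planned ICCs, shifts of 1 to 3 points occur within a single arm; the between-arm difference moves by less than one point.

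It is also fair to say that a working correlation is commonly left to the analysis plan. Its absence is not the fault here. It is named in the remedy because the sentence has to be rewritten in any case.

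**Conclusion.** The point holds as a contradiction in the specification of the primary model, repeated through Section 11.3 and Appendix E. It should be corrected, but its numerical effect is modest. At the largest planned ICC the odds ratio for 50% versus 35% is 0.538 marginally and 0.522 conditionally, with the same null and no change in sample size or stated power. Gaps of 11% and 25% in the log odds ratio need ICCs of 0.10 and 0.20. Section 11.2 allows that the ICC could turn out somewhat larger than 0.05, but it plans for no such value.

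For dentin extension, the between-arm difference moves about 0.4 to 0.8 points at ICC 0.05. This rests on the assumed slope, on equal dentin rates in the arms, and on a normally distributed practitioner effect on the logit scale.

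**What to change.** Delete the mixed-model and random-effect wording from Section 11.3 and from four paragraphs of Appendix E: the opening, operative treatment, dentin extension and clinical predictors. The exploratory practitioner-level analysis of variance at the end of Appendix E is a different model and can stay.

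State one primary model:

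- Logistic GEE with practitioner as the cluster and robust standard errors.
- Study arm as a fixed effect. Region, the randomisation stratum, is included whether or not it is significant. The practitioner's pre-intervention opening rate is a covariate.
- An independence working correlation for dentin extension, so that each opened lesion counts equally.
- Marginal proportions by arm and risk differences with 95% confidence intervals, averaged over the covariates so that they remain population quantities.
- If wanted, a logistic mixed model as a named sensitivity analysis, with its estimation method.

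The cost is wording only. The pre-intervention data are already collected, and no visit, data item or sample-size figure changes.

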2 INTRODUCTION: BACKGROUND INFORMATION AND SCIENTIFIC RATIONALE

2.1 Background Information

A topic of interest mentioned numerous times among practitioners is the management of "questionable" or "suspicious" occlusal caries lesions (SOCL). SOCLs can be defined as occlusal surface areas where visual, tactile, and radiographic signs are insufficient to definitively diagnose caries but where some of these signs are present¹. Although this problem is faced by many practitioners, there has been little careful clinical research and no evidence-based assessments regarding this common clinical problem¹⁻².

It is not clear what proportion of SOCLs are, in fact, active dentinal carious lesions. Only three studies have examined the issue, and their results do not resolve the question³⁻⁵. Clinical excision of lesions demonstrated that 51% had penetrated the dentin³, while histologic examinations found the percentages to be $41\%^4$, and $44\%^5$. Over a two-year observation period, one-half of the originally identified SOCLs were followed with no intervention, except when the lesion was deemed to have progressed to a definitive caries lesion with dentinal involvement. At the end of this two-year observation period, only 16% of the lesions that were followed were deemed to have progressed⁵. Additionally, a recent study on early occlusal lesions found that approximately $\frac{1}{3}$ of lesions that were deemed to be in the dentin were rapidly progressing. This means that $\frac{2}{3}$ of these lesions were slowly progressing (which could mean inactive or in the process of remineralizing)⁶. The results of these studies suggest that non-surgical intervention is the appropriate intervention for a majority of these lesions.

Not surprisingly, the lack of clarity regarding the presence and activity of dentinal caries associated with SOCLs leads to uncertainty among dentists over how to manage these lesions. Our own preliminary studies indicated that there is substantial variation among dentists in decisions regarding the application of preventive measures and also the use of surgical intervention to remove the suspicious tissue and place a restoration⁷.

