4 STUDY DESIGN

The study combines elements of a pre-and post-control group design and a randomized clinical trial. To achieve a sample of 1200 lesions for each of the three arms in the full study, we wish to enroll a total of 90 practitioners (total from all six regions) in the study, each of whom will enroll approximately 40 SOCLs (one lesion/patient), 20 enrolled/completed lesions during the pre-intervention phase, and 20 enrolled/completed lesions during the intervention phase. Thus, the patients enrolled will be representative of the patients with such lesions in the practitioners' offices.

Overview of Study Schedule

There will be a 4-8 month window for practitioner enrollment. When a practitioner has completed the study pre-enrollment requirements and the region has IRB approval s/he will be ready to begin the study. Following enrollment, as part of their study training, practitioners will be trained as follows:

- 1. Study Procedure Training: RCs will provide study procedure training, and practitioners will also receive a training manual which will serve as a reference and will highlight important information.
- 2. Standardization Training Pertaining to SOCLs: During the Study Procedure Training with the practitioner, the RC will provide photographs of teeth with SOCLs and review the clinical characteristics of SOCLs. The RC will answer any questions the practitioner might have about these characteristics. The photographs will be given to the practitioners to place in the operatory for review as needed.
- 3. Device Delivery and Set Up: Practitioners randomized to the device arm following the pre-intervention data collection phase will receive the devices from the RAS, and the RAS will assist with device set up.

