- 4. Device Familiarization: Practitioners randomized to the device arm will familiarize themselves on device use, thus simulating as closely as possible what occurs in practice if dentists purchase devices on their own. Practitioners will "self-train" according to manufacturer's instructions and manufacturer-provided materials (e.g. DVD, Webinar). Practitioners may seek further guidance on device use from their colleagues and may query a manufacturer representative. Device Familiarization will also involve practitioners familiarizing themselves with the devices through unsupervised clinical use with patients. This device familiarization period is anticipated to take approximately four weeks for all practitioners randomized into the device arms.

Before beginning the clinical portion of the study, practitioners will complete pre-study vignettes that require practitioners to make diagnostic decisions with scenarios and photos. They will be asked how likely they would be to choose a specific treatment procedure. This vignette will be completed online. Following the vignette, all practitioners will participate in an approximate 4 week long pre-intervention period without the assistance of a caries detecting device and will enroll patients with at least one lesion. Practitioners will record data for one lesion per patient, which will be determined randomly. If more than one lesion is found in one patient, practitioners will choose the tooth that is closest to the day of the month on the day they are observing the patient. They will choose the tooth in an ascending order. For example, if the day of the month is the fourth, the practitioner will choose the higher number tooth closest to the fourth. Data to be recorded include pre-treatment

findings, a treatment decision, and if necessary, post-treatment findings. If, during the first two weeks of the pre-intervention period, practitioners are unable to enroll five patients with a SOCL, or do not wish to further participate in the study, they may be withdrawn and new practitioner(s) will take their place prior to randomization. The goal for enrollment is approximately 20 enrolled/completed patients each with one SOCL.

Following the pre-intervention period, practitioners will be randomized into one of three arms (Spectra[®], DIAGNOdent[®], and no device). Practitioner randomization will occur after the pre-intervention period.

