Two outcomes are of interest: the proportion of all SOCL that are opened and the proportion of opened SOCL that are carious. Practitioners will each contribute 20 lesions to the study during the intervention period. The planned recruitment of 30 practitioners per group yields a total sample size of 600 lesions per group for the first outcome. The total sample size for the second outcome will be the number of lesions that are opened. Because the study design does not include follow-up of individual patients, patient-level dropout is not anticipated to be a major consideration. Drop-out of practitioners is possible, and could cause the loss of multiple observations, depending on the number of patients that are accrued prior to the practitioner drop-out, up to a maximum of 30. Part of the intent of the pre-intervention run-in period is to identify practitioners who are not likely to succeed in recruiting the required number of patients, and to provide an opportunity for practitioners to drop out prior to randomization, so that they can be replaced without interference to the randomization process. Still, it is possible that practitioners might drop out after randomization. Anticipating a severe situation in which 10% of the initial 30 practitioners in each group drop out prior to contributing any data, power and detectable difference calculations were repeated for 27 practitioners per group, and a total sample size of 540 lesions per group. While this is an extreme and unlikely occurrence, the additional tables provide an indication of the effect of a substantial loss of data.

The expected rates of lesion opening are 50% for no device and 30-35% for the device groups. Differences in rates of opening that would be detectable with 80% power are as follows:

Difference detectable with 80% power				ICC		
	0.00	0.01	0.02	0.03	0.04	0.05
Effective						
sample/group:	600	504	435	382	341	308
Detectable difference						
(%):	9.1	9.9	10.7	11.4	12.0	12.7
Rate in device group						
(%):	40.8	40.1	39.3	38.6	38.0	37.3

Assuming loss of 10% of practitioners per group, without contributing any data to the study:

Difference detectable with 80% power	ICC							
	0 0.01 0.02 0.03 0.04 0.0							
Effective comple/groups	E 40	454	204	244	207	077		
Effective sample/group:	540	454	391	344	307	211		
Detectable difference (%):	9.6	10.4	11.3	12.0	12.7	13.4		
Rate in device group (%):	40.4	39.6	38.7	38.0	37.3	36.6		

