For evaluation of differences in proportions of lesions treated operatively among the intervention groups, the analysis data set will include all SOCLs that are enrolled by the study practitioners. The outcome variable for this analysis will be a dichotomous variable indicating whether the SOCL was treated operatively.

For the comparison of proportions of lesions treated operatively that have caries extending into dentin, the analysis data set will include all SOCLs that were treated operatively by the study practitioners. The outcome variable will be a dichotomous variable indicating whether the lesion extended into the dentin.

Exploratory statistical analyses will be conducted to examine changes in practitioners' rates of operative treatment of lesions during the pre-randomization run-in period versus their rates during the post-randomization intervention period. Further analyses will be conducted to evaluate possible associations between pre- to post-randomization changes in practitioners' rates of operative treatment and variables representing practitioners' perception of changes in the decision-making process. This analysis will be conducted using the practitioner as the unit of analysis, and will utilize a mixed-model analysis of variance approach to evaluate changes in rates and to compare mean changes among the intervention groups, accounting for repeated observations for the practitioners.

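### Primary outcome 1: each practitioner's pre-randomisation operative rate is collected but left out of the primary model, which costs precision but not validity

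*Protocol*

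**What the plan says.** Section 4 presents the study as a blend of a pre/post controlled design and a randomised trial. It asks each practitioner for "20 enrolled/completed lesions during the pre-intervention phase" and a further 20 in the intervention phase, and states: "Practitioner randomization will occur after the pre-intervention period". The baseline rate therefore precedes allocation for every randomised practitioner.

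Section 11.3 fixes the primary model: "These models will include a term representing the individual practitioner as a random effect and study arm as a fixed effect". It allows further control variables, naming only region, if they turn out to be needed. Appendix E repeats the arm and practitioner terms and keeps region only if it is statistically significant.

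The baseline rate has one planned use. Section 11.3 and Appendix E describe exploratory analyses of practitioners' "rates of operative treatment of lesions during the pre-randomization run-in period versus their rates during the post-randomization intervention period", with the practitioner as the unit.

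Section 11.2 rests power on the later phase alone: "Practitioners will each contribute 20 lesions to the study during the intervention period", and "The planned recruitment of 30 practitioners per group yields a total sample size of 600 lesions per group for the first outcome".

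**The concern.** A pre-randomisation measurement of the primary outcome, on the randomised unit, is a natural covariate for a cluster-randomised comparison. Section 2.1 reports from the team's own preliminary work that "there is substantial variation among dentists in decisions regarding the application of preventive measures", and the same sentence extends this to surgical intervention. With 30 practitioners per arm, arms can differ by chance in how readily their dentists operate. The practitioner random effect allows for correlation within a dentist. It does not correct the arm contrast for a difference in baseline rates.

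At stake is the precision of the first primary comparison, and how well it holds up if the ICC lies above the 0.00 to 0.05 range used for planning.

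**Working it through.** **Inputs from the protocol.** Section 11.2 gives m = 20 intervention lesions per practitioner, 30 practitioners (600 lesions) per arm, ICC 0.00 to 0.05, two-sided chi-square tests and a Bonferroni-type adjustment for two comparisons. I take the latter as alpha 0.05/2 = 0.025. On rates it states: "The expected rates of lesion opening are 50% for no device and 30-35% for the device groups". Section 4 gives about 20 pre-intervention lesions. Section 11.2 and Appendix E say the actual contrasts will each be tested at the 95% level, so alpha 0.05 is shown as well.

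**Assumptions.** Let c be the correlation of a practitioner's true rate between the two periods. The protocol gives no value, so I show 0.5, 0.8 and 1.0. ICC 0.10 lies outside the planned range and is also an assumption.

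**Step 1: the plan's own figure.** Design effect = 1 + (20 − 1) × 0.05 = 1.95, and 600/1.95 = 307.7, the protocol's 308. For 50% vs 35% at alpha 0.025 (critical value 2.241):
- SE under the null = √(0.425 × 0.575 × 2/307.7) = 0.0399
- SE under the alternative = √((0.25 + 0.2275)/307.7) = 0.0394
- z = (0.15 − 2.241 × 0.0399)/0.0394 = 1.54, power 93.8% (92.8% with continuity correction)

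The stated figure of about 92% reproduces with no baseline adjustment.

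**Step 2: effect of adjusting.** The correlation of a practitioner's observed pre and post proportions is R = c × m × ICC / (1 + (m − 1) × ICC). Adjustment multiplies the variance of the arm contrast by 1 − R², so the effective sample is divided by 1 − R². At ICC 0.05 and c = 1, R = 1/1.95 = 0.513 and R² = 0.263, giving 307.7/0.737 = 417.

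Power for 50% vs 35%, without continuity correction:

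| ICC | c | R² (variance cut) | Effective lesions per arm | Power, alpha 0.025 | Power, alpha 0.05 |
|---|---|---|---|---|---|
| 0.05 | unadjusted | – | 308 | 93.8% | 96.6% |
| 0.05 | 0.5 | 7% | 329 | 95.3% | 97.5% |
| 0.05 | 0.8 | 17% | 370 | 97.2% | 98.6% |
| 0.05 | 1.0 | 26% | 417 | 98.5% | 99.3% |
| 0.10 | unadjusted | – | 207 | 80.4% | 87.3% |
| 0.10 | 0.5 | 12% | 235 | 85.5% | 91.0% |
| 0.10 | 0.8 | 30% | 297 | 93.0% | 96.1% |
| 0.10 | 1.0 | 48% | 395 | 98.0% | 99.0% |

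**Step 3: lower planned ICCs.** Even with c = 1, the cut is 3% at ICC 0.01, 8% at 0.02 and 15% at 0.03.

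**Step 4: chance imbalance.** At ICC 0.05 and a 50% rate, the between-practitioner variance is 0.25 × 0.05 = 0.0125. The SD of the difference in true baseline rates between two arms of 30 is √(2 × 0.0125/30) = 0.029, or 2.9 points, against an expected effect of 15.

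The formula is for linear adjustment on practitioner means with 20 lesions in each period. It approximates the gain from a logistic model, and the gain shrinks for practitioners with fewer baseline lesions.

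**The case against.** The strongest reply is that nothing here is invalid. A randomised comparison that respects clustering needs no baseline covariate, the stated power is right, covariate lists often belong in an analysis plan, and section 11.3 leaves room for further variables. The points on validity and power stand. The last two do not dispose of the matter. The protocol fixes the model terms in two places and assigns the pre/post data to exploratory work, and its opening for other variables depends on what the data show, so it is not pre-specification.

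Several stronger readings are tempting, and the documents do not support them:
- **Between-dentist variation dominates the error.** Its share of the variance of a practitioner's mean, m × ICC/(1 + (m − 1) × ICC), is 17%, 29%, 38%, 45% and 51% at ICC 0.01 to 0.05. It passes half only at the top of the planned range.
- **Adjustment frees the trial from its ICC assumption.** At c = 0.8 and alpha 0.025, adjusted power still falls from 97% at ICC 0.05 to 84% at ICC 0.20 (an assumed value). At c = 0.5 it falls from 95% to 66%.
- **The baseline rate is the strongest predictor available.** This is plausible, but the protocol gives no pre/post correlation. The devices are meant to change decisions, so stability could be lower in the device arms.
- **The dentin outcome needs the same covariate.** Nothing shows that a practitioner's opening rate predicts dentin extension among opened lesions.

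Adjustment also has a price. A covariate in a logistic model changes what the odds ratio means, while the objective in section 3.1 is a difference in proportions. The fix has to deal with that.

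**Conclusion.** The point holds for primary outcome 1 as a loss of precision and of protection against chance imbalance. It does not show bias or an underpowered design. At ICC 0.05 the variance of the arm contrast could fall by about 7% to 26% for assumed stability of 0.5 to 1.0; at ICC 0.01 the gain is negligible.

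The benefit is larger if the ICC exceeds the planned range. At an assumed 0.10, unadjusted power is about 80% at alpha 0.025, or 87% at the planned per-comparison 0.05. With adjustment it is about 86% to 98%, or 91% to 99%. The unadjusted figures bear out the assurance in section 11.2 that a somewhat larger ICC is tolerable, so the case for change is that the improvement uses data already in hand.

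**What to change.** In section 11.3 and Appendix E, state that the primary model for outcome 1:
- analyses intervention-phase lesions, the set on which section 11.2 bases its 600 per arm. The current text refers to all enrolled lesions without naming a phase.
- includes arm, region (already a stratification factor in section 4) and the practitioner's pre-intervention operative proportion, for example as an empirical logit, all fixed in advance and not selected by significance.
- reports each device-versus-no-device effect as a standardised difference in proportions with a cluster-adjusted confidence interval, alongside the adjusted odds ratio.

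Keep the unadjusted analysis as a sensitivity analysis, and leave the covariates for the dentin outcome as they are on this account. The cost is analysis wording and a standardisation step. No new data are needed and the sample size does not change.
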